### 8.4.2 UNANTICIPATED PROBLEM REPORTING

The investigators will report unanticipated problems (UPs) to the reviewing Institutional Review Board (IRB) and to the lead principal investigator (PI). The UP report will include the following information:

- Protocol identifying information: protocol title and number, PI’s name, and the IRB project number;
- A detailed description of the event, incident, experience, or outcome;
- An explanation of the basis for determining that the event, incident, experience, or outcome represents an UP;
- A description of any changes to the protocol or other corrective actions that have been taken or are proposed in response to the UP.

To satisfy the requirement for prompt reporting, UPs will be reported to the IRB within reasonable timing of the investigator becoming aware of the problem.

### 8.4.3 REPORTING UNANTICIPATED PROBLEMS TO PARTICIPANTS

The IRB at each site will provide guidance to PIs on informing participants regarding UPs as needed.

## 9 STATISTICAL CONSIDERATIONS

### 9.1 STATISTICAL HYPOTHESES

Comparisons will be made between groups 1 and 2 to assess differences in outcomes by type of progestin used, and between groups 1 and 3 to assess differences in outcomes by timing of progestin initiation. The primary outcome is the proportion of women exclusively breastfeeding at 8 weeks postpartum. Differences in baseline demographic characteristics and in variables between groups will be assessed using  $\chi^2$ , Fisher exact, or t-tests as appropriate.

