## 1 PROTOCOL SUMMARY

### 1.1 SYNOPSIS

Title:	Postpartum progestin-only pill use and breastfeeding study
Study Description:	This study will assess the impact of early initiation (less than one week postpartum) and delayed initiation (4 weeks postpartum) of two types of progestin-only contraceptive pills on maternal, breastmilk, and infant outcomes. This is a placebo-controlled randomized controlled trial enrolling dyads of mothers and their newborn babies. We will explore if the type and timing of initiation of pills is acceptable to the user with minimal side effects, impacts the supply or composition of breastmilk, and/or affects infant growth.
Aims:	Specific Aim: To determine whether the type of progestin used (drospirenone in drospirenone-containing progestin-only pills (d-POPs) vs. norethindrone in norethindrone-containing progestin-only pills (n-POPs)) or the timing of progestin initiation (early vs. delayed) affects: Aim 1a Maternal: the duration of exclusive breastfeeding continuation or the rates and types of breastfeeding supplementation over 8 weeks postpartum. Aim 1b Maternal: the proportion of mothers using progestin-only pills at 8 weeks postpartum. Aim 2 Milk: the composition of breastmilk (fat, protein, carbohydrates) at 4 weeks postpartum. Aim 3 Infant: infant growth (weight, length, and head circumference) from birth to 4 weeks.
Study Population:	Postpartum women who delivered an infant within the previous 7 days
Description of Sites	University of California, San Diego (UCSD)
Enrolling Participants:	
Study Duration:	1 year
Participant Duration:	8 weeks

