## 2 INTRODUCTION

### 2.1 STUDY RATIONALE

Drospirenone-containing progestin-only pills (d-POPs) may be an acceptable alternative to Norethindrone-containing progestin-only pills (n-POPs) in the postpartum period when initiated either a week or month after delivery with fewer side effects and no impact on breastfeeding, breastmilk, and infant outcomes. Providing women with more options of safe, effective postpartum (PP) contraception has the potential to reduce unintended pregnancy and short inter-pregnancy intervals, thereby decreasing maternal and infant morbidity and mortality.

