## 3 OBJECTIVES AND ENDPOINTS

Aim	Variable	Description	Source
Maternal Outcomes			
1a	Breastfeeding	Exclusive breastfeeding : own mother's milk via breast or bottle. Predominant breastfeeding : greater than 75% of the infant's diet is their own mother's milk; the remainder of the diet is formula, donated milk, or other supplemental foods Mixed Breastfeeding : 25-75% or more of the infant's diet is their own mother's milk Predominantly supplementing : <25% diet is breastmilk No breastfeeding : infant is not consuming own mother's milk	End of weeks 2-8
1a	Supplementation type	Donated breastmilk, formula, other milks (cow, plant-based, nut), juice, water, cereal, other foods	End of weeks 2-8
1b	Progestin-only pill use	Any use, timing of initiation of POP use (assigned), type of POP (assigned), number of missed pills	End of weeks 2-8.
1b.	Contraception use	Sterilization (male and female), intrauterine devices, subdermal implants, oral contraceptives (combined), condoms (male and female), injectables, emergency contraceptive pills, patches, diaphragms, sponges, cervical caps, spermicidal agents, vaginal rings, withdrawal, fertility awareness, abstinence, and LAM	4 and 8 weeks
	Vaginal bleeding	Number of days of any bleeding and spotting in last month	Estimated at 4 and 8 weeks
	Satisfaction with contraception	Satisfied with method, would recommend method to a friend	4 and 8 weeks
	Pregnancy	Self-reported new pregnancy, pregnancy intendedness, whether planning to continue the pregnancy or not, and pregnancy outcome: continued, terminated, pregnancy loss	4 and 8 weeks
Milk Outcomes			
2	Composition of breastmilk	Fat, protein, carbohydrate (including oligosaccharide) content of milk	4-week breastmilk sample
	Maternal perception of adequate milk supply	Hill and Humenick Lactation Scale	End of weeks 2-8
Infant Outcomes			
3	Change in infant growth	Weight, length, and head circumference	Change between baseline and 4 weeks

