## 4 STUDY DESIGN

### 4.1 OVERALL DESIGN

This is a three-arm, placebo-controlled, double-blinded randomized controlled pilot trial that includes 8 weeks of participation from enrollment to final follow-up.

We hypothesize that the type of progestin used and the timing of progestin initiation will not have clinically meaningful effects on breastfeeding continuation, supplementation, the composition of breastmilk, or infant growth and body composition. In addition, we hypothesize that the timing of progestin initiation will not have a meaningful effect on progestin-only pill (POP) continuation, but that women will be more likely to continue d-POPs compared to n-POPs. Findings from this study will support more women to use progestin-containing contraceptives to prevent unintended pregnancy in the postpartum period with a greater understanding of the safety while breastfeeding.

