## 6 STUDY INTERVENTION

### 6.1 STUDY INTERVENTION

Group 1: Initiation of d-POPs 120-160 hours after delivery (N=10)

Group 2: Initiation of n-POPs 120-160 hours after delivery (N=10)

Group 3: Initiation of d-POPs 4 weeks after delivery (N=10) [placebo starting 120-160 hours, continuing for 28 days]

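### For milk composition and infant growth, Group 1 vs 3 at 4 weeks compares early d-POP with placebo and cannot show effects after a delayed start

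*Combined protocol and SAP*

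**What the plan says.** All references are to the combined protocol and SAP.

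- **The label.** Section 9.1 sets up a comparison "between groups 1 and 3 to assess differences in outcomes by timing of progestin initiation" and makes no exception by outcome. The Specific Aim in 1.1 asks whether "the timing of progestin initiation (early vs. delayed) affects" each of Aims 1a, 1b, 2 and 3. Section 4.1 hypothesises that "the timing of progestin initiation will not have clinically meaningful effects on breastfeeding continuation, supplementation, the composition of breastmilk, or infant growth". Section 2.1 gives as rationale that d-POPs may be acceptable when "initiated either a week or month after delivery with fewer side effects and no impact on breastfeeding, breastmilk, and infant outcomes".
- **When the two outcomes are measured.** Aim 2 is "the composition of breastmilk (fat, protein, carbohydrates) at 4 weeks postpartum", and section 3 gives a single 4-week sample as its source. Infant growth in section 3 is "Change between baseline and 4 weeks". Section 8.1 describes one in-person follow-up visit, at 4 weeks, with no day window. The week-8 contact is an emailed questionnaire.
- **What Group 3 takes.** Section 6.1 gives "placebo starting 120-160 hours, continuing for 28 days" and then d-POP. In 8.1 (Randomization) the first Group 3 pack is entirely placebo, the d-POP start is given as day 28-35, and the start window for the first pack is 120-168 hours, not 120-160.

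**The concern.** A test of early against delayed initiation would normally let the reader compare what happens after each kind of start. For milk composition and infant growth, the only follow-up measurement appears to fall before the delayed group has started the drug. The comparison would then be drug against placebo under a timing label.

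What is at stake is the conclusion. A null Group 1 vs 3 result at 4 weeks would match the wording of the 4.1 hypothesis. Read with the rationale in 2.1, it could be reported as showing that neither an early nor a delayed d-POP start affects milk or growth, although neither outcome is observed after Group 3's planned start. Section 2.2 says the pilot is meant to inform a large trial, which could inherit both the label and the schedule.

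**Working it through.** **Inputs.** Delivery is day 0. First-pack start day s = 5, 6 or 7 (8.1: 120-168 h). Group 3 takes 28 placebo days first (6.1, 8.1). A d-POP pack holds 24 active and 4 inactive tablets (8.1). I take the 4-week visit as day 28. A missed visit may be rescheduled within one week (7.3), so a late visit is taken as day 35.

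**The plan's own figure.** The stated Group 3 d-POP start is day 28-35. The pack schedule gives start = s + 28:
- 120 h: 5.0 + 28 = day 33.0
- 160 h: 6.7 + 28 = day 34.7
- 168 h: 7.0 + 28 = day 35.0

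The pack schedule therefore reproduces only the later end of the stated window (day 33-35). Both readings are carried below.

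**Active d-POP tablets due by the end of day d.** For Group 1, tablets due are T = d - s + 1. The active count is the smaller of T and 24 in the first pack; after day 28 of use it is 24 plus the smaller of T - 28 and 24. For Group 3 it is d - (s + 28) + 1, with a floor of 0 and a cap of 24. If d-POP instead starts on day 28, it is d - 28 + 1 with the same cap.

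| Day | Group 1 (s = 5, 6, 7) | Group 3, pack schedule (s = 5, 6, 7) | Group 3, day-28 start |
|---|---|---|---|
| 28 | 24, 23, 22 | 0, 0, 0 | 1 |
| 35 | 27, 26, 25 | 3, 2, 1 | 8 |
| 56 | 48, 47, 46 | 24, 23, 22 | 24 |

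Counting elapsed days instead of tablets due through the end of the day lowers the day-28 Group 1 counts to 21-23 and the day-35 Group 3 counts on the pack schedule to 0-2. Nothing turns on that choice.

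**Which outcomes are affected.** Milk composition and infant growth have no measurement after the 4-week visit. Breastfeeding status and pill use are collected to week 8, when Group 3 is due 22-24 active tablets. Perceived milk supply is listed for weeks 2-8 in section 3, while the survey text in 8.1 names it only for week 8. Either way it is measured after Group 3's start. Weekly reports at weeks 2-4 precede that start on the pack schedule.

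**Side check on baseline adjustment.** The variance of a baseline-adjusted comparison relative to a change-score comparison is k²(1 - ρ²)/(1 + k² - 2ρk), times 1 + 1/25 for one covariate with 30 women in 3 arms. Here k is the ratio of the 4-week SD to the birth SD. The documents give neither k nor ρ, so I assume k = 1.0-1.2 and ρ = 0.5-0.8:
- k = 1.0: 0.78 (ρ = 0.5), 0.94 (ρ = 0.8)
- k = 1.2: 0.91 (ρ = 0.5), 1.04 (ρ = 0.8)

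The range is from a 22% reduction to a 4% increase.

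**The case against.** Groups 1 and 3 are assigned the same drug and differ in assigned start time. Aim 2 is explicitly about milk at 4 weeks and Aim 3 about growth up to 4 weeks. For outcomes bounded in that way, starting early versus not having started yet is a timing contrast. It also addresses the worry described in 2.2, progestin exposure in the first weeks after delivery. Nothing is hidden: the placebo, its duration and the 4-week time point are all stated. The harm depends on report wording that no section plans. This is a 30-woman feasibility pilot, and no estimate or test changes because of a label.

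Much of this stands, and it rules out several stronger readings:

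- A reader might infer that the comparison is invalid, or that timing language must be barred for these outcomes. The documents do not support that. The randomised contrast is sound, and a statement about early versus not-yet-started use at 4 weeks would be correct.
- A reader might infer that growth is measured only at 4 weeks. It is a change from baseline; only the post-baseline measurement is confined to 4 weeks.
- A reader might infer that the trial's timing question fails as a whole. The primary outcome is at 8 weeks and is not limited in this way.
- A reader might think that baseline adjustment is part of the remedy. It has no bearing on the label, and the enrolment data listed in 8.1 include birth weight but not birth length or head circumference.

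What the objection does not answer is that no section limits the conclusion to early exposure, while 2.1 puts a start at a month on the same footing as a start at a week.

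**Conclusion.** The point holds in a limited form. For milk composition and infant growth, Group 1 vs 3 at an on-time 4-week visit compares 22-24 due active d-POP tablets with 0, or with 1 under a day-28 start. It estimates the effect of assigned early d-POP against assigned placebo. It does not inform effects on milk or growth after a delayed start, and the plan should say so.

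This rests on day 28 as the nominal visit and on tablets due, not tablets taken. A visit a full week late would add 1-3 Group 3 tablets on the pack schedule, or bring the total to 8 under a day-28 start. A few such visits would not provide planned follow-up after a delayed start. The word *assigned* matters because women who do not start the study pills stay in follow-up (7.1), and women may switch method at any time (8.1).

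**What to change.** 1. In 9.1, the 4.1 hypothesis and Aims 2 and 3, define the 4-week Group 1 vs 3 contrast for milk composition and infant growth as *assigned early d-POP vs assigned placebo (d-POP not yet started)*.
2. State that a 4-week result supports a conclusion about early exposure only, and that effects on milk or growth after a delayed start are not observed. Reserve conclusions about delayed initiation for outcomes followed to week 8.
3. Reconcile the d-POP start stated as day 28-35 with 28 placebo days from day 5-7, and the 120-160 h window in 6.1 with the 120-168 h window in 8.1.
4. Optional: report Group 2 vs 3 at 4 weeks as a supplementary norethindrone vs placebo estimate with a 95% confidence interval, which the pairwise provision in 9.4.3 already permits. Record the milk collection date, at home or at the visit, so that late samples can be described.
5. Minor and optional: adjust 4-week infant weight for the recorded birth weight. The gain in precision may be nil.

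The cost is wording edits and a narrower stated conclusion for Aims 2 and 3. The optional items add one supplementary contrast, one recorded date and one adjusted model. No visits or procedures are added.

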## 9.2 SAMPLE SIZE DETERMINATION

The sample size (N=30 in 6 months) was chosen to demonstrate feasibility to enroll 180 women in 36 months at our site during a larger multi-site trial and to successfully complete follow-up.

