## 9.3 POPULATIONS FOR ANALYSES

The following datasets will be utilized for analysis:

- Intention-to-Treat Analysis Dataset: All participants randomized with known outcomes per the 8 week follow up survey.
- Per-Protocol Analysis Dataset: Participants who reported taking their assigned POP throughout the study period and reported follow up data on the 8 week survey.

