## 9.4 STATISTICAL ANALYSES

### 9.4.1 GENERAL APPROACH

### 9.4.2 ANALYSIS OF THE PRIMARY EFFICACY ENDPOINT(S)

A survival analysis will be conducted to to assess time spent exclusively breastfeeding.

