### 9.4.3 ANALYSIS OF THE SECONDARY ENDPOINT(S)

Proportions will be compared using chi-square tests. ANOVAs will be used to calculate means for analysis using all 3 groups and t-tests for any pairwise comparisons.

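### The stated primary outcome is a week-8 proportion, but the only analysis headed as primary is a survival analysis of breastfeeding duration

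*Combined protocol and SAP*

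**What the plan says.** Section 9.1 declares the outcome: "The primary outcome is the proportion of women exclusively breastfeeding at 8 weeks postpartum". It names two comparisons, Group 1 with Group 2 (type of progestin) and Group 1 with Group 3 (timing). The next sentence is general: "Differences in baseline demographic characteristics and in variables between groups will be assessed using" chi-square, Fisher exact or t-tests, as appropriate.

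Section 9.4.2, the primary efficacy endpoint section, is one sentence: "A survival analysis will be conducted to to assess time spent exclusively breastfeeding". It gives no event definition, censoring rule, test, effect measure or week-8 estimate. Section 9.4.1 (general approach) has a heading and no text.

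Four other places bear on the point:

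- Section 9.4.3, secondary endpoints: "Proportions will be compared using chi-square tests".
- Section 9.3, intention-to-treat set: "All participants randomized with known outcomes per the 8 week follow up survey".
- Section 1.1, Aim 1a: "the duration of exclusive breastfeeding continuation or the rates and types of breastfeeding supplementation over 8 weeks postpartum".
- Section 3, endpoint table: breastfeeding is recorded in categories at the end of weeks 2 to 8, and no endpoint is marked as primary.

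**The concern.** A proportion at week 8 asks how many women are exclusively breastfeeding at that point. A survival analysis of time asks how long women continued before stopping. Two arms can agree on one and differ on the other, and a woman who lapses and then returns to exclusive breastfeeding counts differently in each.

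Because the declared outcome and the analysis headed as primary are different quantities, either could be presented as the primary result, and that choice could be made after the data are seen. Section 2.2 says the pilot is meant to inform a large randomized trial, so the ambiguity could carry over into that trial's primary endpoint and sample size.

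**Working it through.** **1. The plan's own figure.** Section 9.2 sets N = 30 on feasibility. The figures agree: 30/6 = 5 women per month, 180/36 = 5 per month, and 3 groups × 10 = 30. No alpha, power, event rate or effect size is given, so N depends on neither version of the primary outcome.

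**2. Which quantity each section fits.**

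| Section | Week-8 proportion | Duration |
|---|---|---|
| 9.1, declared primary outcome | yes | no |
| 9.1, general test sentence | can be read to cover it | no |
| 9.3, intention-to-treat set | yes | no |
| 9.4.2, primary analysis | not named | yes |
| 9.4.3, secondary analyses | chi-square for proportions | not named |
| 1.1, Aim 1a | not named | yes |
| 3, endpoint table | can supply it | can supply it |

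Section 9.3 also works against 9.4.2. A woman with surveys through week 7 but none at week 8 would be dropped, although a survival analysis would censor her at week 7. A woman who stopped at week 3 and missed week 8 would be dropped although her event was observed.

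**3. Can the results differ?** Constructed extreme, 10 per arm, complete follow-up. In arm A, 8 women stop at week 2; in arm B, 8 stop at week 7; 2 in each arm are still exclusive at week 8.

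- Proportions: 2/10 and 2/10, difference 0. Chi-square and Fisher p = 1.00. Newcombe 95% CI -34 to +34 points.
- Mean exclusive time to week 8: A (8×2 + 2×8)/10 = 3.2 weeks; B (8×7 + 2×8)/10 = 7.2 weeks.
- Log-rank, arm A:
  - Week 2: 20 at risk, 8 events, all in A. Expected 8×10/20 = 4; variance 8×(1/2)×(1/2)×(12/19) = 1.263.
  - Week 7: 12 at risk (2 in A), 8 events, none in A. Expected 8×2/12 = 1.333; variance 8×(1/6)×(5/6)×(4/11) = 0.404.
  - Chi-square = (8 - 5.333)²/1.667 = 4.265, p = 0.039.

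Milder patterns narrow the gap:

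- The 8 stops per arm spread over weeks 2–4 in A and 6–8 in B: medians 3 and 7 weeks, log-rank p = 0.086.
- Only 4 of 10 stop per arm, early in A and late in B (60% in both at week 8): log-rank p = 0.73.

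**4. How often would the conclusions differ?** The documents give no stopping rates or alpha, so these are assumptions: constant weekly hazard h = 1 - S^(1/7) over the seven surveys at weeks 2–8, where S is the proportion exclusive at week 8; no dropout or resumption; 10 per arm; two-sided 0.05; uncorrected chi-square; 20,000 simulated trials per row.

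| S in the two arms | Chi-square and log-rank on opposite sides of 0.05 |
|---|---|
| 60% and 60% | 1.4% |
| 60% and 80% | 2.8% |
| 40% and 70% | 4.7% |
| 30% and 80% | 5.9% |

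**5. Resumption.** If 4 of 10 women lapse and 2 of them are exclusive again by week 8, the week-8 proportion is 8/10, while the Kaplan-Meier estimate for first lapse is 6/10. The weekly categories in Section 3 allow this pattern and the plan has no rule for it.

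**The case against.** Section 9.1 is unambiguous about the outcome, and the sentence after it lists tests suited to a proportion. On a fair reading, a test of the primary outcome is planned and only its placement is wrong. No passage declares duration to be the primary outcome; only the heading of 9.4.2 implies it. A Kaplan-Meier curve can also yield a week-8 proportion, and an aim about duration can coexist with a primary outcome at a fixed week. The only contrast with p below 0.05 is contrived, the simulated disagreement is a few percent, and the 0.05 threshold is not in the plan. With 10 women per arm neither analysis can be confirmatory.

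Much of this stands. The general sentence in 9.1 can cover the proportion, the extreme example shows possibility rather than likelihood, and Aim 1a can keep its wording if duration is labelled secondary. The mismatch remains. If 9.1 does supply a test for the proportion, the plan has two candidate primary analyses and ranks neither. Section 9.4.2 plans no week-8 Kaplan-Meier estimate, and such an estimate would equal the week-8 proportion only with complete follow-up and no return to exclusive breastfeeding.

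**Conclusion.** The concern holds. The declared primary outcome and the only analysis headed as primary are different quantities, and no other section reconciles them. This rests on the text alone and not on any assumed rate.

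The numerical consequence is modest. Opposite conclusions at 0.05 occur in about 3% to 6% of simulated trials where the arms differ, and in 1.4% where they do not, under constant stopping rates with no dropout or resumption. Larger divergence needs early stopping in one arm and late stopping in the other, or women who resume. N = 30 is unaffected. It should be fixed because it leaves the primary result open to choice and may pass into the larger trial; it does not undermine the pilot's feasibility purpose.

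**What to change.** Before unblinding, name one primary outcome with its matching analysis. Keeping the outcome in 9.1 is simplest. Suggested text for 9.4.2:

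> The primary outcome is exclusive breastfeeding at the week-8 survey (yes/no). The difference in proportions, with a 95% confidence interval suited to small samples (for example Newcombe), will be estimated for Group 1 versus Group 2 and for Group 1 versus Group 3.

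Then:

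- Say whether exclusive at week 8 means current feeding or uninterrupted since birth, and how women without a week-8 survey enter this analysis.
- Move the survival analysis to 9.4.3 as the secondary analysis for Aim 1a, and define the event.
- State in 9.3 that, for the survival analysis, women without an event are censored at their last completed survey and not excluded for lacking the week-8 survey.

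If the investigators prefer duration as primary, change 9.1 and the 9.3 analysis set instead, and define event and censoring in 9.4.2.

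The cost is a few sentences, with no added women, visits or data. Making duration secondary loses a little information: at an assumed 60% versus 80%, chi-square rejects in 13.1% of simulated trials and log-rank in 15.6%. Either way the result is descriptive: 8/10 versus 6/10 is a difference of 20 points with a Newcombe 95% CI of -19 to +52.
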